22.6 Subject confidentiality

The trial staff will ensure that the participants' anonymity is maintained. The participants will be identified only by initials and a subject's identification number on the CRF and any database. All documents will be stored securely. The study will comply with the Data Protection Act.

23. FINANCING AND INSURANCE/INDEMNITY

The Heartbeat Trust is the Sponsor and it will ensure that every Investigator is covered by a Clinical Trial Insurance, which shall remain in effect for the duration of the Agreement. All Investigators are qualified and practicing physicians and are thus insured by the clinical indemnity scheme.

24. CLINICAL STUDY REPORT AND PUBLICATION POLICY

24.1 Clinical study report

The study report will be drafted by the Clinical Trials Manager of the HBT in compliance with the Sponsor's SOP.

The Sponsor and the Chief Investigator must mutually agree on the final version. One copy of the final report must be dated and signed by the Chief Investigator and the Legal Representative of the Sponsor.

24.2 Publication policy

The results of this study will be published in a high-quality clinical journal. The results of this study may provide the impetus for further research into the management of asymptomatic patients with risk factors for heart failure with LCZ696.

The responsibility for publication of the data obtained from this study lies with the Investigator. Neither the Sponsor, nor any of the study funders, will have any involvement in data collection, data review, data analysis or preparation of the publication manuscript or in the decision to submit for publication. Submission of any publication manuscript may take place only with the permission of [name], Consultant Cardiologist, and [name], Director of Research, St. Vincent's University Hospital, Dublin 4.

25. STUDY PLANNING AND SCHEDULE

The project milestones are as follows:

1. Clinical trial application to the HPRA
2. St Vincent's University Hospital Ethics application
3. Selection of suitable subjects from the STOP-HF data base and STOP-HF Service in St Michael's Hospital
4. Informed consent from subjects
5. Recruitment of patients and inclusion in the study
6. Final evaluation
7. Data analyses
8. Manuscript preparation
9. Publication and presentation of results

25.1 Timelines and study duration

Start date: FPFV: 16 December 2015

End date:

- 18-month treatment period: LPFV: December 2018. FPLV: Oct 2017 and LPLV: December 2020
- 9- month follow-up (regression) substudy: FPFV: July 2019; LPLV: May 2021

Study Report date: CSR to be made available within 12 months after study completion.

26. APPENDICES

Appendix 1. Montreal Cognitive Assessment (MoCA)

Montreal Cognitive Assessment Basic_MoCA.pdf

Appendix 2. Standardised Mini-Mental State Examination SMMSE)

Standardised MMSE.pdf

Appendix 3. EuroQoL (EQ-5D-5L) Health Questionnaire

Subject study ID:	Subject initials:	
Date of test:	Visit number:	
 Baseline	 9 months	 18 months

Under each heading, please tick the ONE box that best describes your health TODAY.

MOBILITY

- I have no problems in walking about
- I have slight problems in walking about
- I have moderate problems in walking about
- I have severe problems in walking about
- I am unable to walk about

SELF-CARE

- I have no problems washing or dressing myself
- I have slight problems washing or dressing myself
- I have moderate problems washing or dressing myself
- I have severe problems washing or dressing myself
- I am unable to wash or dress myself

USUAL ACTIVITIES (e.g. work, study, housework, family or leisure activities)

- I have no problems doing my usual activities
- I have slight problems doing my usual activities
- I have moderate problems doing my usual activities
- I have severe problems doing my usual activities
- I am unable to do my usual activities

PAIN / DISCOMFORT

- I have no pain or discomfort
- I have slight pain or discomfort
- I have moderate pain or discomfort
- I have severe pain or discomfort

I have extreme pain or discomfort

ANXIETY / DEPRESSION

I am not anxious or depressed

I am slightly anxious or depressed

I am moderately anxious or depressed

[figure not shown]
I am severely anxious or depressed

I am extremely anxious or depressed

- We would like to know how good or bad your health is TODAY.
- This scale is numbered from 0 to 100.
- 100 means the best health you can imagine.
0 means the worst health you can imagine.
- [name] an X on the scale to indicate how your health is TODAY.
- Now, please write the number you marked on the scale in the box below.

YOUR HEALTH
TODAY =

The best health
you can imagine

The worst health
you can imagine

Appendix 4. Montreal Cognitive Assessment (MoCA) Version 3. Administration and Scoring Instructions

The Montreal Cognitive Assessment (MoCA) was designed as a rapid screening instrument for mild cognitive dysfunction. It assesses different cognitive domains: attention and concentration, executive functions, memory, language, visuoconstructional skills, conceptual thinking, calculations, and orientation.

Time to administer the MoCA is approximately 10 minutes.

The total possible score is 30 points; a score of 26 or above is considered normal.

1. Alternating Trail Making:

Administration: The examiner instructs the subject: *"Please draw a line, going from a number to a letter in ascending order. Begin here [point to (1)] and draw a line from 1 then to A then to 2 and so on. End here [point to (E)]."*

Scoring: Allocate one point if the subject successfully draws the following pattern: 1 –A- 2- B- 3- C- 4- D- 5- E, without drawing any lines that cross. Any error that is not immediately self-corrected earns a score of 0.

2. Visuoconstructional Skills (Cylinder):

Administration: The examiner gives the following instructions, pointing to the cylinder: *"Copy this drawing as accurately as you can, in the space below"*.

Scoring: One point is allocated for a correctly executed drawing.

- Drawing must be three-dimensional
- All lines/ovals are drawn
- No line is added
- The horizontal lines are relatively parallel.
- The objects at the end must be ovals rather than circles.
- The horizontal lines must touch the top/bottom of the ovals.

A point is not assigned if any of the above-criteria are not met.

3. Visuoconstructional Skills (Clock):

Administration: Indicate the right third of the space and give the following instructions: *"Draw a clock. Put in all the numbers and set the time to ten past nine"*.

Scoring: One point is allocated for each of the following three criteria:

- Contour (1 pt.): the clock face must be a circle with only minor distortion acceptable (e.g., slight imperfection on closing the circle);
- Numbers (1 pt.): all clock numbers must be present with no additional numbers; numbers must be in the correct order and placed in the approximate quadrants on the clock face; Roman numerals are acceptable; numbers can be placed outside the circle contour;
- Hands (1 pt.): there must be two hands jointly indicating the correct time; the hour hand must be clearly shorter than the minute hand; hands must be centred within the clock face with their junction close to the clock centre.

A point is not assigned for a given element if any of the above-criteria are not met.

4. **Naming:**

Administration: Beginning on the left, point to each figure and say: *"Tell me the name of this animal"*.

Scoring: One point each is given for the following responses: (1) donkey (or mule); (2) pig (or hog); (3) kangaroo.

5. **Memory:**

Administration: The examiner reads a list of 5 words at a rate of one per second, giving the following instructions: *"This is a memory test. I am going to read a list of words that you will have to remember now and later on. Listen carefully. When I am through, tell me as many words as you can remember. It doesn't matter in what order you say them."*

[name] a check in the allocated space for each word the subject produces on this first trial. When the subject indicates that (s)he has finished (has recalled all words), or can recall no more words, read the list a second time with the following instructions: *"I am going to read the same list for a second time. Try to remember and tell me as many words as you can, including words you said the first time."*

Put a check in the allocated space for each word the subject recalls after the second trial. At the end of the second trial, inform the subject that (s)he will be asked to recall these words again by saying, *"I will ask you to recall those words again at the end of the test."*

Scoring: No points are given for Trials One and Two. Scoring is based on the delayed recall trial.

6. **Attention:**

Forward Digit Span: Administration: Give the following instruction: *"I am going to say some numbers and when I am through, repeat them to me exactly as I said them"*. Read the five number sequence at a rate of one digit per second.

Backward Digit Span: Administration: Give the following instruction: *"Now I am going to say some more numbers, but when I am through you must repeat them to me in the backwards order."* Read the three number sequence at a rate of one digit per second.

Scoring: Allocate one point for each sequence correctly repeated, (N.B.: the correct response for the backwards trial is 4-7-1).

7. **Vigilance:**

Administration: The examiner reads the list of letters at a rate of one per second, after giving the following instruction: *"I am going to read a sequence of letters. Every time I say the letter A, tap your hand once. If I say a different letter, do not tap your hand"*.

Scoring: Give one point if there is zero to one errors (an error is a tap on a wrong letter or a failure to tap on letter A).

8. **Serial 7s:**

Administration: The examiner gives the following instruction: *"Now, I will ask you to count by subtracting 7 from 80, and then, keep subtracting 7 from your answer until I tell you to stop."* Give this instruction twice if necessary.

Scoring: This item is scored out of 3 points. Give no (0) points for no correct subtractions, 1 point for one correct subtraction, 2 points for two-to-three correct subtractions, and 3 points if the participant successfully makes four or five correct subtractions.

Count each correct subtraction of 7 beginning at 80. Each subtraction is evaluated independently; that is, if the participant responds with an incorrect number but continues to correctly subtract 7 from it, give a point for each correct subtraction. For example, a participant may respond "72 – 65 – 58 – 51 – 44" where the "72" is incorrect, but all subsequent numbers are subtracted correctly. This is one error and the item would be given a score of 3.

9. **Sentence repetition:**

Administration: The examiner gives the following instructions: *"I am going to read you a sentence. Repeat it after me, exactly as I say it [pause]: **She heard his lawyer was the one to sue after the accident.**"*

Following the response, say: *"Now I am going to read you another sentence. Repeat it after me, exactly as I say it [pause]: **The little girls who were given too much candy got stomach aches.**"*

Scoring: Allocate 1 point for each sentence correctly repeated. Repetition must be exact. Be alert for errors that are omissions (e.g., omitting "too much") and substitutions/additions (e.g., ". . . his lawyer sued after . . ."; "the girls"), altering plurals, etc.).

10. **Verbal fluency:**

Administration: The examiner gives the following instruction: *"Tell me as many words as you can think of that begin with a certain letter of the alphabet that I will tell you in a moment. You can say any kind of word you want, except for proper nouns (like Peter or Paris), numbers, or words that begin with the same sound but have a different suffix, for example, love, lover, loving. I will tell you to stop after one minute. Are you ready? [Pause] Now, tell me as many words as you can think of that begin with the letter B. [time for 60 sec]. Stop."*

Scoring: Allocate one point if the subject generates 11 words or more in 60 sec. Record the subject's response in the bottom or side margins.

11. **Abstraction:**

Administration: The examiner asks the subject to explain what each pair of words has in common, starting with the example: *"Tell me how an orange and a banana are alike".* If the subject answers in a concrete manner, then say only one additional time: *"Tell me another way in which those items are alike".* If the subject does not give the appropriate response (fruit), say, *"Yes, and they are also both fruit."* Do not give any additional instructions or clarification. After the practice trial, say: *"Now, tell me how an eye and an ear are alike".*

Following the response, administer the second trial, saying: *"Now tell me how a trumpet and a piano are alike".* Do not give any additional instructions or prompts.

Scoring: Only the last two item pairs are scored. Give 1 point to each item pair correctly answered. The following responses are acceptable:

- eye-ear = sensory organs, parts of the head, parts of the body;
- trumpet-piano = musical instruments, you can play them.

The following responses are **not** acceptable: eye-ear = parts of the face.

12. Delayed recall:

Administration: The examiner gives the following instruction: *"I read some words to you earlier, which I asked you to remember. Tell me as many of those words as you can remember."* Make a check mark (✓) for each of the words correctly recalled spontaneously without any cues, in the allocated space.

Scoring: Allocate 1 point for each word recalled freely without any cues.

[figure not shown]
13. Orientation:

Administration: The examiner gives the following instructions: *"Tell me the date today".* If the subject does not give a complete answer, then prompt accordingly by saying: *"Tell me the [year, month, exact date, and day of the week]."* Then say: *"Now, tell me the name of this place, and which city it is in."*

[figure not shown]
Scoring: Give one point for each item correctly answered. The subject must tell the exact date and the exact place (name of hospital, clinic, unit). No points are allocated if subject makes an error of one day for the day and date.

TOTAL SCORE: Sum all sub-scores listed on the right-hand side. Add one point for an individual who has 12 years or fewer of formal education, for a possible maximum of 30 points. A final total score of 26 and above is considered normal.

Appendix 5. Adverse Event Handling. Investigator Responsibilities. Flow Diagram

Appendix 6. Adverse Event Handling. Sponsor Responsibilities. Flow Diagram

Appendix 7. Clinically notable laboratory values and vital signs

Clinically notable laboratory abnormalities for selected tests based on a percent change from baseline:

Haematology

RBC count	>50% increase	>20% decrease
Haemoglobin	>50% increase	>20% decrease
Haematocrit	>50% increase	>20% decrease
WBC count	>50% increase	>50% decrease
Platelet count	>75% increase	>50% decrease

Blood Chemistry

ALT (SGPT)	>150% increase	
AST (SGOT)	>150% increase	
BUN	>50% increase	
Creatinine	>50% increase	
Total bilirubin	>100% increase	
CPK	>300% increase	
Alkaline phosphatase	>100% increase	
Sodium	>5% decrease	
Potassium	>20% increase	>20% decrease
Chloride	>10% increase,	>10% decrease
Calcium	>10% increase,	>10% decrease
Uric acid	>50% increase	

Appendix 8. Treatment guidelines

Treatment guidelines for hyperkalaemia (serum K⁺ > 5.2 mEq/L)

General principles: It is recommended that any subject with a serum K⁺ > 5.2 mEq/L following randomization may require frequent checks of potassium concentration until it is clear that the potassium concentration is stable and not rising into the range of concern (> 5.5 and < 6.0 mEq/L) or potential danger (> 6.0 mEq/L).

Investigators should not randomize a subject with a serum K⁺ > 5.2 mEq/L at Visit 1 (screening) and follow the other measures outlined below if K⁺ increases to values > 5.2 mEq/L after randomization.

Corrective action recommended for management of hyperkalaemia

K⁺ > 5.2 and ≤ 5.5 mEq/L

- If necessary, confirm potassium concentration was obtained in a non-haemolysed sample. If it is confirmed that questionable results were obtained from haemolysed specimen, redraw blood sample for K⁺ measurement and caution should be taken to minimize the incidence of haemolysis by proper blood sample collection and handling
- Reinforce low potassium diet and restriction of food/drinks with high potassium content (e.g. orange juice, melon, bananas, low-salt substitutes, etc.)
- Review medical regimen (including dietary supplements and over-the-counter medications) for agents known to cause hyperkalaemia. Consider reduction in dose or discontinuation of these agents:
 - Confirm that potassium-sparing diuretics and potassium supplements aren't being used
 - Salt substitutes
 - Non-steroidal anti-inflammatory drugs (NSAIDs)
 - Cyclo-oxygenase-2 (COX-2) inhibitors
 - Trimethoprim and trimethoprim-containing combination products such as trimethoprim/sulfamethoxazole
 - Herbal Supplements: (for example, Noni juice, alfalfa (Medicago sativa), dandelion (Taraxacum officinale), horsetail (Equisetum arvense), nettle (Urtica dioica), milkweed, lily of the valley, Siberian ginseng, hawthorn berries)

K⁺ > 5.5 and ≤ 6.0 mEq/L

- If necessary, confirm potassium concentration was obtained in a non-hemolyzed sample
- Apply all measures outlined for K⁺ 5.2 and ≤ 5.5 mEq/L
- Repeat K⁺ measurement after 1-3 days
- Discontinue the study drug if a repeated K⁺ > 5.5 mEq/L

K⁺ > 6.0 mEq/L

- Immediately discontinue study drug
- Confirm potassium concentration in a non-haemolysed sample
- Urgently evaluate subject and treat hyperkalaemia as clinically indicated
- Apply all measures outlined for K⁺ > 5.2 and ≤ 6.0 mEq/L

Guidelines for the management of hypotension

1. Treatment should not be initiated if systolic BP <100mmHg at screening or baseline. A lower starting dose (Level 1) should be considered for patients with systolic BP ≥100 to 110mmHg.
2. Investigator should monitor blood pressure closely throughout the study
3. If systolic BP falls to ≤95mmHg (or symptomatic hypotension occurs at any BP):
 - Correct any treatable cause, e.g. hypovolemia
 - If symptomatic hypotension persists, consider down titrating or stopping other hypotensive medications, and/or study drug as appropriate.
 - If symptomatic hypotension persists during two consecutive office visits or as judged by the Investigator, discontinue the study drug.

Guidelines for the management of renal dysfunction

General principles: Some subjects may develop renal dysfunction after study drug administration. Two types of response to serum creatinine increase are described:

Surveillance situation

If, at any moment after recruitment, serum creatinine increases by ≥50% from baseline (Visit 1), the Investigator will check for potentially reversible cases of renal dysfunction such as:

- NSAID intake, diuretics, antibiotics, or other treatments known to affect creatinine
- Volume decrease
- Urinary infection
- Urinary tract obstruction
- Study medication

The Investigator should consider discontinuing any medication known to affect the renal function and should repeat the serum creatinine after 5-7 days.

Action situation

If serum creatinine >3.0 mg/dL or increases by ≥100% from baseline (Visit 1), the Investigator will discontinue study drug and check for potentially reversible causes of renal dysfunction (see above). Thereafter, serum creatinine should be monitored until its resolution.

Appendix 9. PARABLE. Nine-month follow-up study

1. Objectives and endpoints

The overall objective of the nine-month follow-up study is to evaluate if the treatment effects observed during the 18-month PARABLE study persist nine-months after study drug discontinuation (see Exploratory Objective No 4 in Section 10.1).

Secondary and exploratory endpoints shall be evaluated in this sub-set of subjects (see Exploratory Endpoint No 10 Section 10.2).

2. Eligibility criteria

All PARABLE participants that completed the 18-month follow-up period, and did not discontinue the study drug prematurely, will be eligible for inclusion in the follow-up study.

3. Informed Consent

The procedure for obtaining informed consent is outlined in Section 22.5 of the main PARABLE protocol. Informed consent shall be obtained from the participant prior to any study related assessment or procedure been conducted using the Participant Information Leaflet and Informed Consent Form for the follow-up study (HBT-GCP-FM-39).

4. Assessments and procedures

The following assessments and procedures will be carried out at the nine-month follow-up visit in the same manner they were conducted during the main PARABLE study (see section 12.4) of the study protocol).

- Physical exam
 - Vital size (BP and pulse, height, weight and waist/hip circumference)
 - Biochemistry
 - Urea & Electrolytes (U&E) including eGFR
 - Liver Function Tests (LFT)
 - Alkaline Phosphatase
 - Lipid profile
 - HbA1c
 - Iron studies
 - Haematology
 - Full blood count
- Urine for second messenger cGMP and ANP*
- Blood for biomarkers*
- Serum BNP and NT-proBNP
- Ambulatory blood pressure monitoring
- 12-lead ECG
- Echo-Doppler studies

- QOL questionnaire (EuroQol) and two cognitive function assessment tools

*cryovials will be labelled with the following information:

- PAR-XXXX (where XXXX is the participants PARABLE study ID)
- The date the sample was taken
- The type of sample (e.g. whole blood, lithium heparin, urine etc)
- Timepoint: 9M-FU

REFERENCES

1. Ledwidge, M., et al., *Natriuretic peptide–based screening and collaborative care for heart failure: The stop-hf randomized trial*. JAMA, 2013. **310**(1): p. 66-74.
2. Huelsmann, M., et al., *PONTIAC (NT-proBNP Selected PreventiOn of cardiac eveNts in a populaTion of dIabetic patients without A history of Cardiac disease): A Prospective Randomized Controlled Trial*. Journal of the American College of Cardiology, 2013. **62**(15): p. 1365-1372.

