44. Impact of LCZ696 on biomarkers of angiogenesis, hypoxia, cardiac remodelling, cell adhesion, platelet activation, coagulation, chemotaxis, catabolic stress, inflammation and fibrosis which will be assessed using Olink CVIII proseek panel, between baseline and 18 months
45. Difference between treatment groups in incidence of atrial fibrillation/flutter, paroxysmal supraventricular tachycardia and other atrial or ventricular arrhythmias measured non-invasively in a sub-set of subjects over 5-7 days using continuous ECG monitoring

46. Pharmacogenetic responses to therapy dependent on polygenic risk score of blood pressure, atrial fibrillation, atrial dilatation associated gene variants and established pharmacogenetic gene variants of natriuretic peptide pathway and sacubitril (e.g. NPPB, NPPA, NPRC (NPR3), MME, FURIN, CLCN, DPP4, KLKB1, CES1 gene variants) at 18 months
47. Subgroup analyses on primary outcome and secondary endpoints (pre-specified subgroups include above and below median age and BMI, eGFR (above and below 90mls/min); gender, obesity, vascular disease, hypertension, diabetes, atrial fibrillation/flutter, valve disease)
48. Use of circulating metabolomics profile to identify responders to LCZ696 (based on primary and secondary endpoints)
49. Evaluation of secondary and exploratory endpoints in a sub-set of subjects, 9 months after completing therapy with IMP (extension analysis/9 months follow-up sub-study)
50. Evaluation of primary and secondary endpoints in total follow up period and prior to Covid19 restrictions implemented (13 March 2020)
51. Additional novel and established biomarkers outlined above measured in serum, plasma, or urine profiling using proteomic, transcriptomic, epigenomic, and metabolomic approaches
52. Evaluation of health economic analysis using cost-benefit analysis and cost-benefit analysis.

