12.2 Baseline visit (Visit 2)

Eligible patients will undergo a 36-hour washout period if they were previously taking an ACE inhibitor[†] and be randomized to one of two arms for 18 months:

[1] Intervention arm: LCZ696 100mg twice daily, titrated after two weeks to 200mg twice daily on top of usual medical care or

[2] Control arm: ARB (valsartan) 80mg twice daily, titrated after two weeks to 160 twice daily on top of usual medical care.

[†]LCZ696 must not be initiated until 36 hours after taking the last dose of ACE inhibitor.

*A starting dose of LCZ696 50mg twice daily or valsartan 40mg twice daily will be used for subjects not currently taking an ACE inhibitor or an ARB, and/or for subjects previously taking low doses of these agents (as per Investigator judgement). A lower dosing regimen should also be used for subjects with a systolic BP of ≥ 100 mm to 110mmHg at screening or baseline. The dose of LCZ696 and valsartan will be doubled every 2 to four weeks to the target dose of 200mg and 160mg twice daily for LCZ696 and valsartan respectively, as tolerated by the subject.

All subjects will be reviewed two weeks after dose titration for tolerability issues (e.g. symptomatic hypotension, hyperkalaemia, renal dysfunction). In cases of poor tolerability, temporary down-titration of study drug, co-medication or discontinuation will be considered (see Appendix 10).

Additional medications or interventions will be administered at the discretion of the attending physician. The use of an ACE inhibitor an ARB concomitantly with the study drug after randomisation is strictly prohibited.

The Investigator shall complete a 'Wallet Card' for each patient. Patients will be advised to carry the card with them at all times and to present the card to medical personnel should they require any medical care outside the study while participating in the study.

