12.3 Follow up visits (Visits 3-11)

Table 2 outlines the schedule of clinical assessments, blood sampling, imaging and follow-up that will apply in PARABLE. Follow-up visits will take place in the STOP-HF Service, St Michael's Hospital, Dun Laoghaire.

A follow-up visit will also take place two weeks after each dose titration (i.e. at week two and four and six).

If any subject refuses to return for these assessments or is unable to do so, every effort should be made to contact him/her by telephone and these attempts should be recorded in the subject's paper case report form (pCRF). If one visit is postponed or brought forward, it should not result in the next visit being postponed or brought forward. The next visit, if at all possible, should adhere to the original time schedule.

Table 2. Study assessments and procedures

Visit number	1	2	3	4	5	6	7	8	9	10	11	12
Assessment	Wk-2 Screening	D0 Baseline	Wk 2	Wk 4	Wk 6	Wk 13 / Mth 3	Wk 26 / Mth 6	Wk 39 / / Mth 9	Wk 52 / Mth 12	Wk 65 / Mth 15	Wk 78 / Mth 18 (EOS)	Mth 27 (Optional sub-study)
			± 3d	± 3d	± 3d	± 7d	± 7d	± 7d	± 7d	± 7d	± 7d	± 28
Assessment of eligibility	X											X
Pregnancy test (WOCBP)	X	X	X	X	X	X	X	X	X	X	X	X
Informed consent	X											X
Randomisation		X										
Medical history	X											
Physical exam	X	X	X	X	X	X	X	X	X	X	X	X
Height (H) and weight (W)		H/W						W			W	H/W
Waist/hip circumference		X						X			X	X
Vital signs (BP and pulse)	X	X	X	X	X	X	X	X	X	X	X	X
Natriuretic peptide	X [#]	X	X	X	X	X	X	X	X	X	X	X
Biomarkers		X			X	X	X	X	X	X	X	X
U&E, LFT, Alk phos	X (no alk phos)	X	X	X	X	X	X	X	X	X	X	X
Haematology	X	X						X			X	X
eGFR	X	X						X			X	X
HbA1c, lipid profile, iron studies		X						X			X	X
cGMP (urinary)		X			X	X		X			X	X
ABPM		X						X			X	X
Electrocardiography (ECG)		X						X			X	X
Doppler echocardiography	X [*]	X [†]						X			X	X
Cardiac MRI [‡]		X									X	
Questionnaires ^{**}		X						X			X	X
Concomitant medications	X	X	X	X	X	X	X	X	X	X	X	
Adverse events			X	X	X	X	X	X	X	X	X	X
Dispense medication		X	X	X	X	X	X	X	X	X		
Drug accountability			X	X	X	X	X	X	X	X	X	
Holter monitor (optional)											X	

*Source: results of these assessments may be filed in the Subject Study File on the original source document (questionnaires) or a copy of the source document (e.g. laboratory report, Echo report, ECG (this must be a copy of the original), ABPM printout etc.)

‡ Echo may be needed at Visit 1 if one hasn't been performed in the previous six months.

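### The nine-month follow-up sub-study can give only limited evidence on persistence: its medication recording is contradictory, it promises cMRI endpoints it does not measure, and it states no comparator for a selected subset

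*Combined protocol and SAP*

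**What the plan says.** The aim in Appendix 9 is to "evaluate if the treatment effects observed during the 18-month PARABLE study persist nine-months after study drug discontinuation". The endpoints are given in one sentence, "Secondary and exploratory endpoints shall be evaluated in this sub-set of subjects", and endpoint 49 in section 10.2 has the same scope: "Evaluation of secondary and exploratory endpoints in a sub-set of subjects, 9 months after completing therapy with IMP". Neither narrows the list to what is measured at that visit.

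Entry is by completion of treatment: "All PARABLE participants that completed the 18-month follow-up period, and did not discontinue the study drug prematurely, will be eligible". Table 2 marks the visit (Visit 12, month 27) as optional. The protocol gives no planned number of participants for it, and neither Appendix 9 nor section 16 describes an analysis.

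The row of Table 2 labelled "Concomitant medications" is marked at Visits 1 to 11 and blank at Visit 12. The Appendix 9 list of assessments does not contain the item either. Section 12.4.16, in contrast, has the investigator ask about medication changes at every visit and makes no exception. During treatment, section 12.2 states: "The use of an ACE inhibitor an ARB concomitantly with the study drug after randomisation is strictly prohibited". Section 13.1 says that study drug takes the place of a patient's ACE inhibitor or ARB.

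Section 12.4.15 and Table 2 place cMRI at baseline and month 18 only.

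**The concern.** To learn whether an effect outlasts treatment, one needs the same measure before and after stopping, in the same people, with knowledge of what they took in between. Each of the three is incomplete here.

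Both arms contain valsartan, so both lose their trial renin-angiotensin blockade when study drug ends. Some patients may restart an ACE inhibitor or ARB during the nine months that follow, and no visit is scheduled in that interval. If restart is not captured at Visit 12, a preserved or lost arm difference cannot be attributed to persistence, regression or new therapy, and the gap cannot be filled at analysis.

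The open-ended endpoint list commits the sub-study to results it has no images to produce. With no comparator named, the completers' month-27 contrast could also be set against the month-18 contrast in all randomised participants. That would mix a change of population with a change over time.

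**Working it through.** The sub-study has no stated sample size, power or effect size, so there is no figure of the plan's own to reproduce. The check is mainly a comparison of passages.

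**1. Concomitant medication at Visit 12**

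| Place | What it implies for Visit 12 |
|---|---|
| Table 2, medication row | Not scheduled (marked at Visits 1 to 11 only) |
| Table 2, adverse-event row directly below | Scheduled, so the Visit 12 column is in use |
| Appendix 9 list | Not listed |
| Section 12.4.16 | Asked at every visit |

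The two places specific to Visit 12 agree with each other and conflict with the general section. No passage asks for the start date of an ACE inhibitor or ARB after month 18, or says how such use enters an analysis.

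**2. Secondary endpoints (section 10.2) against what is measured at month 27**

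- Measure repeated: 1 (echo E/e'), 2 (echo LAVI), 7 (ABPM pulse pressure), 8 (NT-proBNP) = 4.
- Needs cMRI, not done: 3, 4, 5, 6, and 10 (per-protocol analysis of the cMRI primary) = 5.
- Defined over 18 months: 9 (time to first event) = 1.

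4 + 5 + 1 = 10, so 5 of 10 cannot be evaluated. Endpoint 10 re-analyses the primary, so the distinct secondary cMRI measures lost are four (3 to 6). Exploratory endpoints 11 to 18, eight in all, are also cMRI measures.

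The Appendix 9 cross-references do not settle the list. It points to exploratory objective 4 and exploratory endpoint 10. In section 10, persistence is exploratory objective 9, the sub-study is endpoint 49, and number 10 is the per-protocol primary.

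**3. Population and comparator**

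Section 13.9 keeps participants who stop study drug in follow-up, so the month-18 population includes them. Appendix 9 excludes them. No text names the comparison to be made.

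Illustration of what a cross-population comparison could do. Assumptions: a fraction p stops study drug in each arm, those who stop show no month-18 effect, and the completers' contrast is 2.0 mL/m² (the difference used in section 16.2). The protocol gives no figure for p.

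All-randomised contrast = 2.0 × (1 − p):

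- p = 10%: 2.0 × 0.9 = 1.8 mL/m²
- p = 20%: 2.0 × 0.8 = 1.6 mL/m²
- p = 30%: 2.0 × 0.7 = 1.4 mL/m²

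At p = 20%, completers whose contrast fell from 2.0 to 1.6 by month 27 (0.4/2.0 = 20% lost) would match the all-randomised month-18 value and appear to show full persistence. A same-patient comparison avoids this.

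**4. Precision, for context only**

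Attendance is not stated. Assume that the SD of echo LAVI change at month 27 lies between 4.7 (section 16.2, month 9) and the 5.0 used there. The 95% half-width of the arm contrast is 1.96 × SD × √(2/n per arm):

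- n = 25: 2.61 to 2.77 mL/m²
- n = 50: 1.84 to 1.96 mL/m²
- n = 100: 1.30 to 1.39 mL/m²

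With 50 per arm or fewer, the interval is about as wide on each side as the 2.0 mL/m² difference, or wider.

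**The case against.** **Medication.** Section 12.4.16 has no exception for Visit 12, Appendix 9 refers back to section 12.4, and its list is not exhaustive: it also omits adverse events and the pregnancy test, both marked at Visit 12 in Table 2. This stands to the extent that a reader who infers that no medication is recorded after study drug stops goes further than the documents. It does not remove the conflict. Section 12.4.16 is also written around interactions with study drug.

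**Restart as part of the outcome.** Therapy begun after study drug stops can be regarded as a consequence of stopping, so the arm contrast stays interpretable as a treatment-policy effect. Blinding covers the whole study (section 13.1), and the trial ends at the last sub-study visit (section 13.11), so nothing suggests that restart would differ by arm. That is fair. The question asked is nevertheless whether effects "persist nine-months after study drug discontinuation", and even balanced restart bears on that reading.

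**Comparator.** A reader might infer that the subset will be compared with the full-trial effect. No passage says so. A within-subset comparison is neither planned nor excluded; the defect is the silence.

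**Size of bias.** It is tempting to attach a LAVI figure to unrecorded restart. The documents do not support one. The 2.6 mL/m² from the earlier 36-week heart-failure trial is the LCZ696 arm's reduction, the valsartan arm rose by 0.3 mL/m² (section 9.3), and no restart rate is given for either arm.

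**Importance.** This is an exploratory objective at an optional visit, and the main 18-month analysis is untouched. That stands.

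**Conclusion.** The point holds in limited form. Three things need correction: a contradiction on whether medication is recorded at Visit 12; an endpoint promise that exceeds the measurements (5 of 10 secondary endpoints and exploratory endpoints 11 to 18); and a post-randomisation drug-completer subset with no stated comparator or analysis.

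It would be too strong to say that the sub-study is unable to address persistence or must reach a wrong answer. Echo LAVI, E/e', NT-proBNP and ABPM are measured at months 18 and 27 and can be compared by randomised arm within the subset, as exploratory evidence.

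No size in mL/m² is claimed for the medication problem. The population and precision figures are illustrations that rest on the assumed stopping fractions, effects, SDs and attendance. The medication finding assumes that the blank Visit 12 cell in Table 2 is as intended; the Appendix 9 list agrees with it. The correction is worth making because it costs little and because medication not captured at the visit cannot be supplied by the analysis.

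**What to change.** - Reconcile Table 2, Appendix 9 and section 12.4.16 by marking concomitant medication at Visit 12 in both the table and the list, with drug, dose and start date since Visit 11. For visits already held, hospital records (source documents under section 18.1) may supply part of this.
- Limit the Appendix 9 endpoints and endpoint 49 to what Visit 12 measures: echo, ABPM, ECG, natriuretic peptides, biomarkers, laboratory values and questionnaires. Correct the two cross-references to section 10.
- State the analysis: baseline-adjusted arm contrasts at month 18 and at month 27 in the same sub-study patients, with the difference between the two contrasts and its confidence interval. Report ACE inhibitor and ARB use after month 18 by arm.
- Describe attenders against non-attenders by arm, and label the result exploratory in a subset selected after randomisation.

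The cost is one mark in Table 2, revised wording in Appendix 9 and endpoint 49, and a few minutes per visit. The downside is a more modest sub-study conclusion.
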